
trial PP population is considered.

The trial plans to test the hypothesis of "superiority" of therapy with the investigational product vs. placebo therapy. The following indicator was chosen as the primary efficacy criterion: "The magnitude of change in the patient's **mRS** (Modified Rankin Scale) score at the end of therapy vs. baseline (in points)".

In the case of a superiority trial, the null hypothesis (H_0) and the alternative hypothesis (H_1) are formulated as follows:

$$H_0: \varepsilon = \mu_{\tau} - \mu_p \leq \delta, H_1: \varepsilon > \delta, \delta > 0, \text{ where}$$

- ε - true difference between the value of the primary efficacy index (μ_{τ}) in the group of patients taking the investigational product (T) and the value of the primary efficacy index (μ_p) in the group of patients taking placebo,
- δ - the boundary of "superiority" of therapy with the investigational product compared to placebo therapy by the primary efficacy indicator.

To prove superiority of therapy with the investigational product compared to placebo therapy, the lower bound of the 95% (or 97.06% in the case of a phase II trial) one-sided confidence interval (CI) for the difference in values of the primary efficacy criterion ($\mu_{\tau} - \mu_p$) must be greater than δ , where $\delta > 0$, i.e. CI must fall within the interval $(\delta, +\infty)$.

Interval (quantitative) data will be described using: arithmetic mean, standard deviation, median, lower (25%) and upper (75%) quartiles, minimum, maximum and coefficient of variation. Categorical (qualitative) data will be described using frequencies, percentages and/or fractions.

To compare quantitative data distributed according to the normal distribution law, it is planned to use standard parametric criteria: Student's t-test for dependent/independent samples, analysis of variance (ANOVA) for repeated measures.

It is planned to use standard nonparametric criteria to compare quantitative data distributed according to a law other than normal: Mann-Whitney U-test, Wilcoxon T-test, Friedman's test. The test for conformity to the normal law of distribution will be carried out using the Shapiro-Wilk test. Comparisons of frequencies of indicators between treatment groups will be made using Pearson's χ^2 test or Fisher's exact test.

Analysing safety data:

Safety parameters will be analysed in the ITT population.

Safety data will be analysed using the methods outlined for the assessment of

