The trial plans to conduct an interim analysis of the data, based on which a decision will be made whether to end the trial (if the trial objective is met) or to enroll the additional number of patients needed to confirm the efficacy of the IP, followed by pooling of all data for the final analysis. The choice of this approach¹ is due to the change in the design of the planned clinical trial, duration of use and dosages of the investigational product compared to the previously conducted clinical trial (EPICA).

In the first phase, an interim analysis of the primary endpoint data will be performed on all randomized patients (304 patients) at the end of the trial:

- If the required power $\geq 80\%$ is achieved, a 95% one-sided confidence interval for the difference in values of the primary efficacy criterion ($\mu_T - \mu_P$) will be used to prove the hypothesis of 'superiority'; the results obtained will be analysed and used to write the final clinical trial report.
- If the calculated power is less than 80 per cent, the sample size will be recalculated based on the data obtained after the first stage to achieve a trial power of 80 per cent, using a correction for genus I error α ($\alpha = 0.0294$)². A protocol amendment will then be submitted to the Ministry of Health and, once approval is granted, the necessary additional number of patients will be enrolled, followed by pooling of all data for final analysis and writing of the final clinical trial report. A 97.06% one-sided confidence interval for the difference in values of the primary efficacy criterion ($\mu_T - \mu_P$) constructed from pooled patient data, i.e. obtained from the first and second stage results, using $\alpha = 0.0294$, will be used to prove the hypothesis of 'superiority'. The final clinical trial report will be written using data from all patients.

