9.8. Significance level and power of the criterion

The level of significance (genus I error α) was chosen to be 0.05 (5%) and the power of the criterion was chosen to be at least 0.8 (80%).

Since an interim data analysis is planned, a genus I error correction approach α ($\alpha = 0.0294$)¹ will be used to prove the hypothesis of "superiority" of investigational product therapy over placebo therapy on the primary efficacy criterion.

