9.9. Statistical criteria for trial discontinuation

In the first phase, at the end of the trial, all randomized patients (304 patients) will undergo an interim analysis of the data for the primary endpoint²:

- If the required power $\geq 80\%$ is achieved, a 95% one-sided confidence interval for the difference in values of the primary efficacy criterion ($\mu_t - \mu_p$) will be used to prove the hypothesis of 'superiority'; the results obtained will be analysed and used to write the final clinical trial report.
- If the calculated power is less than 80 per cent, the sample size will be recalculated based on the data obtained after the first stage to achieve a trial power of 80 per cent, using a correction for genus I error α ($\alpha = 0.0294$). A protocol amendment will then be submitted to the Ministry of Health and, once approval is granted, the necessary additional number of patients will be enrolled, followed by pooling of all data for final analysis and writing of the final clinical trial report. A 97.06% one-sided confidence interval for the difference in values of the primary efficacy criterion ($\mu_t - \mu_p$) constructed from pooled patient data, i.e. obtained from the first and second stage results, using $\alpha = 0.0294$, will be used to prove the hypothesis of 'superiority'. The final clinical trial report will be written using data from all patients.

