Plan for statistical analysis of efficacy and safety parameters

Safety parameters

Safety and tolerability will be assessed throughout the trial (from first use of the investigational product/placebo) using the following data:

1. AE/SAE reports data,
2. Physical examination data, vital signs (BP, HR, respiratory rate, body temperature),
3. Indicators of laboratory analyses and instrumental methods of examination.

A conclusion on the safety of the investigational product will be made after statistical evaluation of all AEs, including serious SAEs with at least a possible association with the use of the investigational product.

Applicable significance level: probability of a 1st kind of error is set at 5%. As an interim analysis of the primary endpoint data is planned, a genus I error correction approach α ($\alpha = 0.0294$) will be used to prove the hypothesis of "superiority" of investigational product therapy vs. placebo therapy for the primary efficacy criterion.

2. Purpose of data statistical analysis

The purpose of the development of this Statistical Analysis Plan is to describe the planned analysis of efficacy and safety data in the "Prospective international multicentre randomized double-blind placebo-controlled parallel-group clinical trial to evaluate the efficacy and safety of Mexidol® solution for intravenous and intramuscular administration, 50 mg/ml (RPC PHARMASOFT LLC, Russia) and Mexidol® FORTE 250 film-coated tablets, 250 mg (RPC PHARMASOFT LLC, Russia) in their sequential use in patients in the acute and early recovery periods of ischaemic stroke (IS)" under protocol #PHS-APIS-004-MEX-SOL-TAB, version 1.3 dated 07.06.2021, for inclusion of the results in the Clinical Trial Report.

The results obtained according to the planned statistical analysis of the data presented in this document will be used in the submission of the registration dossier for the drug to the regulatory authorities, as well as in the writing of publications on the materials of the conducted clinical trial.

The trial will be conducted in accordance with the Protocol, in strict compliance with applicable regulatory requirements, including but not limited to:

- Constitution of the Russian Federation;
- Current version of the Federal Law of the Russian Federation dated 21 November 2011 No. 323-FZ "On the Fundamentals of Health Protection of Citizens in the Russian Federation";

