According to the results of the EPICA clinical trial, the mean value of the change in the mRS score at the end of the course of therapy relative to the baseline level in the group of therapy with the investigational product was (mean (SD)) 278 (0.755) scores, in the placebo group - 1.986 (0.847) scores 2.278 (0.755) scores, in the group of placebo therapy - 1.986 (0.847) scores, the difference (Mexidol® - placebo) is 0.292 scores, 95% confidence interval for the difference (Mexidol® - placebo) is (0.027, 0.556). The "superiority" boundary (δ) was chosen as the lower boundary of the confidence interval constructed for the difference (Mexidol® - placebo). Thus, $\delta = 0.027$ scores.

To test the hypothesis of "superiority" of therapy with the investigational product compared with placebo therapy at a significance level of $\alpha = 0.05$ (5%) to ensure power $1-\beta = 0.8$ (80%) , the sample size was calculated for the primary efficacy criterion given the parallel design, a 1:1 randomization scheme (i.e., $k=1$ - the ratio of sample sizes of the groups n_T/n_p , i.e. $k=1$ - the ratio of sample sizes in the groups n_T/n_p), the expected difference in efficacy between the compared drugs $\varepsilon = 0.292$ and with a mixed standard deviation (SD) of the in-group efficacy $\sigma = 0.802$ scores.

The formula [Chow Sh.-Ch., Shao J., Wang H., 2008] was used in the calculation:

$$n_T = n_p = \frac{(1 + 1/k) \times (z_\alpha + z_\beta) \times \sigma^2}{(\varepsilon - \delta)^2}$$

Version 1.0 of 12.11.2021

Protocol-Specific Version for Protocol #PHS-
APIS-004-MEX-SOL-TAV. version 1.3 dated
07.06.2021

CONFIDENTIAL

page 28 of 58

Plan for statistical analysis of efficacy and safety parameters

where z_α and z_β - quantiles of the normal distribution $N(0,1)$ (mean: 0, standard deviation: 1).

The minimum number of patients completing the trial according to the protocol must be at least $N=2x 114=228$ patients (114 patients per group).

Given the possible attrition of patients in the trial, it is planned to **randomize 304 patients**, of whom **at least 228 should complete the trial according to the Protocol**.

The trial plans to conduct an interim analysis of the data, based on which a decision will be made whether to end the trial (if the trial objective is met) or to enroll the additional number of patients needed to confirm the efficacy of the drug, followed by pooling of all data for the final analysis.

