Secondary efficacy and safety endpoints and their changes will be presented using descriptive statistics by visit and therapy group. On trial visits, qualitative (dichotomous) measures will be compared between groups on the basis of Pearson's χ^2 test, if the frequency

Plan for statistical analysis of efficacy and safety parameters

of a feature in at least one subgroup is 5 or less, Fisher's exact test (or Fisher-Freeman-Galton test for tables of arbitrary dimensionality). Differences with p values of <0.05 will be considered statistically significant.

To compare quantitative data distributed according to the normal distribution law, it is planned to use standard parametric criteria: Student's t-test for dependent/independent samples, analysis of variance (ANOVA) for repeated measures.

It is planned to use standard nonparametric criteria to compare quantitative data distributed according to a law other than normal: Mann-Whitney U-test, Wilcoxon T-test, Friedman's test.

Benjamini-Yekuteli correction will be used for multiple statistical hypothesis testing.

A one-sided test will be applied to analyse the primary endpoint and two-sided statistical tests will be applied to analyse all secondary endpoints.

Scatter plots (boxplots) will be presented for all quantitative measures of efficacy and safety. Data whose distribution differs from normal at least at one visit in one of the groups will be presented as median and interquartile range; data whose distribution is normal at all visits will be presented as mean \pm standard deviation.

Pharmacodynamic effects will be analysed in a subpopulation of patients participating in the evaluation of the pharmacodynamic effects of the investigational therapy.

The resulting data will be analysed using the methods outlined for the application of the efficacy data assessment.

The p-level values <0.05 will be considered statistically significant.

The trial did not include interim statistical analyses.

The application of methods of statistical analysis of the obtained data will be determined by their nature, type and features of their distribution. The feasibility of using a number of statistical methods will be assessed after the completion of the data set, due to the unknown nature of their distribution, sample homogeneity, etc. During the course of the analysis, it is possible to expand the list of methods used if it is necessary for qualitative data processing.

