At the stage of statistical data processing, additional analyses of the efficacy and/or safety of investigational product/placebo in subpopulations of patients of different age groups can be performed.

The final report will include data on all patients included in the trial, including those who dropped out at any time without explanation. No missing data will be supplemented.

12. Interim analysis

The trial plans to conduct an interim analysis of the data, based on which a decision will be made whether to end the trial (if the trial objective is met) or to enroll the additional number of patients needed to confirm the efficacy of the drug, followed by pooling of all data for the final analysis. The choice of this approach is due to the change in the design of the planned clinical trial, duration of use and dosages of the investigational product compared to the previously conducted clinical trial (EPICA).

In the first phase, an interim analysis of the primary endpoint data will be performed on all randomized patients (304 patients) at the end of the trial:

- If the required power $\geq 80\%$ is achieved, a 95% one-sided confidence interval for the difference in values of the primary efficacy criterion ($\mu_t - \mu_p$) will be used to prove the hypothesis of 'superiority'; the results obtained will be analysed and used to write the final clinical trial report.

If the calculated power is less than 80 per cent, the sample size will be recalculated based on the data obtained after the first stage to achieve a trial power of 80 per cent, using a correction for genus I error α ($\alpha = 0.0294$). A protocol amendment will then be submitted to the Ministry of Health and, once approval is granted, the necessary additional number of patients will be enrolled, followed by pooling of all data for final analysis and writing of the final clinical trial report. A 97.06% one-sided confidence interval for the difference in values of the primary efficacy criterion ($\mu_t - \mu_p$) constructed from pooled patient data, i.e. obtained from the first and second stage results, using $\alpha = 0.0294$, will be used to prove the hypothesis of 'superiority'. The final clinical trial report will be written using data from all patients.

13. Table templates

Table 2. Results of assessment of normality of distribution of indicators (template)

Indicators	Stage	Investigational Products					
		Mexidol®			Placebo		
		W	P	Distribution	W	P	Distribution

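### The significance level and the 80% power gate for the only confirmatory test are not stated consistently or completely in the protocol and SAP

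*Protocol*

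**What the plan says.** **Operative rule.** Protocol 9.1 says that "an interim analysis of the primary endpoint data will be performed on all randomized patients (304 patients) at the end of the trial". Protocol 9.1 and 9.9 and SAP 12 then give two branches:

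- Calculated power of at least 80%: superiority is judged with a one-sided 95% confidence bound.
- Otherwise: "If the calculated power is less than 80 per cent, the sample size will be recalculated based on the data obtained after the first stage". More patients are enrolled after an approved amendment, and the pooled data are judged with a one-sided 97.06% bound (0.0294).

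The protocol synopsis and 9.7.2 carry the same split, but describe the second case as "97.06% in the case of a phase II trial".

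**Places that differ.**

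- Protocol 9.8 sets the overall level at 5%, then continues: "Since an interim data analysis is planned, a genus I error correction approach", with 0.0294 to be used for the superiority claim. No stage is named.
- SAP 1 does the same: "As an interim analysis of the primary endpoint data is planned, a genus I error correction approach".
- The hypothesis paragraph of Protocol 9.1 and SAP 7 give only the one-sided 95% bound, with no stage-2 level.
- SAP 9 states: "The trial did not include interim statistical analyses". SAP 8 states: "The trial plans to conduct an interim analysis of the data, based on which a decision will be made whether to end the trial", and SAP 12 describes that analysis.
- SAP Table 4, footnote 2, gives 97.06% for stage 2, in line with the operative rule. Footnote 4 concludes superiority from the upper bound of a two-sided 95% interval and attributes this to the protocol, which uses a one-sided lower bound.

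**Gate.** The documents give the 80% threshold and a footnote to a paper on sequential designs for crossover bioequivalence studies. They do not say which effect, SD, alpha or analysis set produces the calculated power. The look is described on all 304 randomised patients, possibly only as timing, while Protocol 9.7.2 and SAP 11 make the PP population primary.

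**The concern.** This is the trial's one confirmatory test, so its level and decision bound should have a single reading. A statistician working from Protocol 9.8 or SAP 1 as written would use 0.0294 at stage 1. One working from Protocol 9.9 or SAP 12 would use 0.05. One filling in Table 4 by its footnote 4 would use a bound on the wrong side of the estimate. For some results these give different verdicts on the same data.

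The gate matters separately. It decides whether the trial ends or enrols more patients. With its inputs unstated, that decision could be settled after the data have been seen.

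**Working it through.** **Inputs** (Protocol 9.1): expected difference 0.292, margin δ = 0.027, SD 0.802, 1:1 allocation, one-sided α 0.05, power 80%. Normal quantiles: 1.645 (0.05), 1.890 (0.0294), 0.842 (80% power).

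**1. The plan's own figure.** n per arm = 2 × (1.645 + 0.842)² × 0.802² / (0.292 − 0.027)² = 113.3, so 114. This reproduces, and shows that the trial was sized at one-sided 0.05. With 1.890 in place of 1.645 the result is 136.7, so 137.

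**2. What the level changes.** Three sizes per arm are used: 114 (the stated minimum of 228), 126 (304 randomised at the earlier EPICA trial's per-protocol rate in Protocol 2.3.2: 304 × 124/150 / 2 = 125.7) and 152 (no loss from 304).

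SE = 0.802 × √(2/n). Power = Φ(0.265/SE − z). Smallest successful observed difference = 0.027 + z × SE.

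| n per arm | SE | Power at 0.05 | Power at 0.0294 | Threshold at 0.05 | Threshold at 0.0294 |
|---|---|---|---|---|---|
| 114 | 0.1062 | 80.2% | 72.7% | 0.202 | 0.228 |
| 126 | 0.1010 | 83.6% | 76.8% | 0.193 | 0.218 |
| 152 | 0.0920 | 89.2% | 83.9% | 0.178 | 0.201 |

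The share of trials landing between the two thresholds, at a true effect of 0.292, is the difference in power: 7.5%, 6.8% and 5.3%. At a true effect equal to δ it is 5% − 2.94%, about 2%.

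**3. What the gate inputs change** (gate α 0.05, true effect 0.292, true SD 0.802).

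- *Observed effect enters.* Passing needs z ≥ 1.645 + 0.842 = 2.486, an observed difference of at least 0.291, 0.278 or 0.256. Any trial that passes has already cleared the 95% bound, so that bound never decides anything. P(extend) = Φ(2.486 − 0.265/SE) = 50%, 45%, 35%.
- *Planned effect with observed SD enters.* Passing needs an SD of at most 0.265 / (2.486 × √(2/n)) = 0.805, 0.846 or 0.929. From the chi-square distribution on 2n − 2 degrees of freedom, P(extend) = 46%, 11%, under 0.01%.

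The gate α matters too. With the planned effect and SD at 114 per arm, calculated power is 80.2% at 0.05 (pass) but 72.7% at 0.0294 (fail).

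**4. SAP Table 4 footnote 4.** With a true difference of zero, P(upper two-sided 95% bound > 0.027) = P(Z > 0.027/SE − 1.96). At 114 per arm this is P(Z > −1.71) = 95.6%. At 152 it is P(Z > −1.67) = 95.2%. Taken literally, an ineffective treatment would meet the criterion about 95% of the time.

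**5. Type I error under the written branches** (true effect = δ, one test per path, observed-effect gate, total re-sized by ((1.890 + 0.842)/z₁)², where z₁ is the stage-1 statistic). Numerical integration gives 3.4% with the total capped at twice stage 1 and 3.9% with no cap, if trials with an observed difference at or below δ stop. It reaches 5.35% only if those trials also extend without limit, which no passage directs.

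**The case against.** The strongest reply is that the specific rule settles the general one. The synopsis, Protocol 9.1, 9.7.2 and 9.9 and SAP 12 agree on 95% at stage 1 and 97.06% at stage 2, if the synopsis and 9.7.2 wording is taken to mean stage 2. Protocol 9.8 and SAP 1 both open by fixing the overall level at 5%, and elsewhere the correction to 0.0294 appears only in the extension branch. They can fairly be read as loose references to stage 2. The gate is also not wholly open: a method is cited, Table 4 puts a stage-1 power column beside the observed difference, PP is named for the proof of superiority, and extension needs an approved amendment. The SAP was written for protocol version 1.3 and the protocol supplied is 1.5, so some differences between the two documents may reflect timing.

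Much of this stands. The intended rule can be inferred, and the disputed window is narrow. But 9.8 and SAP 1 tie 0.0294 to an interim being planned, not to an extension occurring. The conflicts between Protocol 9.8 and 9.9, and between SAP 9 and SAP 8 and 12, lie inside one document, so versioning does not explain them. Footnote 4 cannot be reconciled with any other passage. The amendment step fixes neither the stage-1 level nor the gate inputs.

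A reader might infer that the scheme inflates type I error. The documents do not support that: each path has one test, and the calculation above shows no material excess. Nor is the introductory remark about ending the trial once its objective is reached a rival rule of testing at 0.05 and then again at 0.0294. In Protocol 9.1 and SAP 12 it is followed by the operative branches, which govern.

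**Conclusion.** The point holds as a defect of specification in the decision rule, to be settled before unblinding. As written, the level at stage 1 has two readings, one SAP sentence denies the interim analysis, one table footnote states a criterion that would be met about 95% of the time with no effect, and the gate cannot be computed without choices that the documents leave open.

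The level conflict changes the verdict in about 5% to 7% of trials at the planned effect, and reading 0.0294 into stage 1 lowers power at 114 per arm from 80.2% to 72.7%. The gate is the larger practical matter: at 152 per arm the choice of input moves the chance of extension from 35% to under 0.01%, though at 114 per arm the two choices are close (50% and 46%).

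These figures assume SD 0.802, a true effect of 0.292 where stated, and a normal approximation. The 152 per arm case assumes no loss from the PP population, which is optimistic against the planned fall from 304 to 228.

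**What to change.** Before unblinding, keep both written branches and make every section say the same thing:

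- Protocol 9.8 and SAP 1: state that 0.0294 applies only to the pooled stage-2 test.
- Protocol 9.1 (hypothesis paragraph) and SAP 7: add the stage-2 level.
- Synopsis and Protocol 9.7.2: replace the reference to a phase II trial with stage 2.
- SAP 9: delete the sentence denying interim analyses.
- SAP Table 4 footnote 4: replace with *superiority is concluded if the lower bound of the one-sided 95% CI (97.06% at stage 2) for the difference in mean mRS change exceeds 0.027*.
- Protocol 9.1 and 9.9 and SAP 12: write the gate as *calculated power uses the PP population, difference 0.292, δ 0.027, the observed pooled SD and one-sided α 0.05; if it is below 80%, the total is recalculated with the same difference and SD at 0.0294*.

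By simulation with t-tests, this gives type I error of about 4.2% at 114 per arm to 5.0% at 152, and power of 81.5% to 89.1%. When the trial extends, the median total is 1.2 to 1.3 times stage 1.

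The edits are wording only, but one consequence should be stated openly. With the difference fixed at 0.292, only the SD can trigger extension, so the trial no longer adapts to a smaller observed effect. The plan justifies its interim analysis by changes in design, duration and dosage since the earlier trial, so the sponsor should accept that consequence knowingly.

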Patient group	Group	$\mu \pm SD$	Efficacy evaluation:	
			95% CI for the difference in mean ($\mu_{\text{Mex.}} - \mu_p$)	Comparison between groups
ITT population (n = 144)	Group I (Mexidol®, n = 72)	2.278 ± 0.755	DM = 0.292 (0.027; 0.556)	p = 0.029 (Mann-Whitney U-test)
	Group II (Placebo, n = 72)	1.986 ± 0.847		

According to the results of the EPICA clinical trial, the mean value of the change in the mRS score at the end of the course of therapy relative to the baseline level in the group of therapy with the investigational product was (mean (SD)) 2.278 (0.755) points, in the placebo group - 1.986 (0.847) points 2.278 (0.755) points, in the group of placebo therapy - 1.986 (0.847) points, the difference (Mexidol® - placebo) is 0.292 points, 95% confidence interval for the difference (Mexidol® - placebo) is (0.027, 0.556). The "superiority" boundary (δ) was chosen as the lower boundary of the confidence interval constructed for the difference (Mexidol® - placebo). Thus, $\delta = 0.027$ points.

To test the hypothesis of "superiority" of therapy with the investigational product compared with placebo therapy **at a significance level of $\alpha = 0.05$ (5%) to ensure power $1-\beta = 0.8$ (80%)**, the sample size was calculated for the primary efficacy criterion given the parallel design, a 1:1 randomization scheme (i.e., $k = 1$ - the ratio of sample sizes of the groups n_T/n_p), the expected difference in efficacy between the compared products $\varepsilon = 0.292$ and with a mixed standard deviation (SD) of the in-group efficacy $\sigma = 0.802$ points.

The formula [Chow Sh.-Ch., Shao J., Wang H., 2008] was used in the calculation:

$$n_T = n_R \frac{\frac{(1 + 1/k) * (z_\alpha + z_\beta)^2 * \sigma^2}{(\varepsilon - \delta)^2}}{\frac{2 * (1.6449 + 0.8416)^2 * 0.802^2}{(0.292 - 0.027)^2}} \approx 114 \text{ people/gr,}$$

where z_α and z_β - quantiles of the normal distribution $N(0,1)$ (mean: 0, standard deviation: 1).

The minimum number of patients completing the trial in accordance with the protocol must be at least $N = 2 * 114 = 228$ patients (114 patients per group).

Given the possible attrition of patients in the trial, it is planned to **randomize 304 patients**, of whom **at least 228 should complete the trial according to the Protocol**.

Given the potential dropout of patients during the Screening phase, approval is planned for a clinical trial with a total of **336 screened patients**.

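### The interim is introduced as ending the trial once its objective is met, but the written rule stops on calculated power and has no stage-1 superiority test below 80%

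*Protocol*

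**What the plan says.** **Purpose of the interim.** Protocol 9.1 says that after the interim "a decision will be made whether to end the trial (if the trial objective is met"), the alternative being to enrol more patients and pool all data. SAP 8 and SAP 12 say the same. Protocol 9.1 and 9.7.2 define the objective: the lower limit of the one-sided interval for the difference in mRS change must exceed δ = 0.027.

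**Operative rule.** Protocol 9.1, Protocol 9.9 and SAP 12 carry the same two branches.
- Calculated power at least 80%: superiority is judged on a one-sided 95% interval and the trial is reported.
- Calculated power below 80%: "If the calculated power is less than 80 per cent, the sample size will be recalculated based on the data" from stage 1 (Protocol 9.9; SAP 12 reads the same), at α = 0.0294. An amendment is filed, patients are added, and superiority is judged on a one-sided 97.06% interval from pooled data. No stage-1 test or success stop appears.

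**Left open.** Neither document says which difference, SD, α or population enters the calculated power. The interim is described on all 304 randomised patients, whereas the sizing concerns per-protocol completers ("The minimum number of patients completing the trial in accordance with the protocol must be at least" 228), and the PP population is primary. SAP 9 also states that the trial has no interim statistical analyses, which contradicts SAP 12.

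**The concern.** The introduction makes stopping depend on the result; the branches make it depend on power. These are different events. A trial can clear the superiority bound while its calculated power is below 80%. For that trial the introduction says end and the branches say enrol. Protocol 9.9, the section on discontinuation criteria, does not repeat the introduction, so read alone it points only to enrolment.

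At stake are further stroke patients randomised, half of them to placebo, after the plan's own criterion has been met; the delay of an amendment and a new enrolment round; and a small chance that a result already achieved is lost in the pooled analysis. In addition, the 80% quoted in Protocol 9.1 is the power of a plain single-stage test. It is not the chance of concluding at that size under this rule.

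**Working it through.** **Inputs.** Protocol 9.1: "the difference (Mexidol® - placebo) is 0.292 points"; δ = 0.027; SD 0.802; 1:1 allocation; power 80%; α = 0.05. SAP 9: "A one-sided test will be applied to analyse the primary endpoint".

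**The plan's own figure.** n per arm = 2 × (1.6449 + 0.8416)² × 0.802² / (0.292 − 0.027)² = 113.3, so 114 per arm and 228 in total. This reproduces. At 114 per arm the SE is 0.802 × √(2/114) = 0.1062, the expected Z is 0.265/0.1062 = 2.495, and single-stage power is Φ(2.495 − 1.645) = 80.2%.

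**Where introduction and branches disagree.** If power is computed from the observed effect, reaching 80% requires Z ≥ 1.645 + 0.842 = 2.486.
- 95% bound met: difference above 0.027 + 1.645 × 0.1062 ≈ 0.202.
- Power gate passed: difference at least 0.027 + 2.4865 × 0.1062 ≈ 0.291.

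Between about 0.202 and 0.291 the objective is met but the branches extend the trial. Example: Z = 1.9 (difference 0.229) also clears the 97.06% bound (Z > 1.890). Re-sizing gives 114 × (2.731/1.9)² ≈ 236 per arm, or 2 × (236 − 114) = 244 more patients.

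**How often, with the design assumptions true.** Calculated power is undefined, so two readings are used, with the gate at α = 0.05.
- A: observed effect and SD. Stage-1 success = Φ(2.495 − 2.486) = 50.3%. Bound met but extended = 80.2 − 50.3 = 29.9%. Also clearing 97.06% = Φ(2.495 − 1.890) − 50.3% = 72.7 − 50.3 = 22.4%.
- B: planned 0.265 and observed SD. The gate passes if the observed SD is at most 0.265/(2.4865 × √(2/114)) = 0.8046, which has probability 54%. The other B figures are simulated.

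| Evaluable per arm | Reading | Single-stage success | Stage-1 success under rule | 95% bound met but extended |
|---|---|---|---|---|
| 114 | A | 80% | 50% | 30% |
| 114 | B | 80% | 44% | 36% |
| 152 | A | 89% | 65% | 24% |
| 152 | B | 89% | 89% | about 0% |

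At 114 per arm under B, 32% also clear the 97.06% bound. At 125 per arm (EPICA's 124 of 150 per-protocol rate applied to 304), 28% (A) or 10% (B) meet the 95% bound and are extended. If the gate itself used α = 0.0294, stage-1 success at 114 per arm would be 41% (A) or 3% (B).

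**Whole rule, simulated at 114 per arm.** Overall success including stage 2 is about 99% (A, with an assumed cap of 500 or 2000 per arm, since the plan gives none; median total about 518 when extended) or 82% (B; median total about 292 when extended). Trials that meet the stage-1 bound and then fail the pooled test: 1.2% (A) or 1.6% (B). False-positive rate of the written rule: about 4.7% (A) or 4.2–4.4% (B).

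**The case against.** **Power does not collapse.** A reader might infer that the trial's power falls from 80% to 44–50%. It does not. Those figures are the chance of concluding at stage 1 with the minimum 228 completers. Extended trials are tested again, and overall success stays at about 80% or above.

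**228 is the unfavourable size.** The rule names 304 patients, and 228 is a minimum. At 152 per arm the loss is smaller, and under reading B it disappears. That stands. But Protocol 9.4 imputes nothing, so 152 per arm is an upper limit, and the primary population is PP.

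**Extension is not clearly mandatory.** A reader might infer that the plan as a whole compels enrolment. The introduction says otherwise; Protocol 9.8 applies α = 0.0294 to proving superiority without confining it to stage 2; and SAP Table 4 has a superiority column with no power condition. These support stopping on the result. However, a Table 4 footnote reserves the 97.06% interval for stage 2, and no text places a test in the low-power branch. What remains is a conflict within the plan.

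**The α correction is not wasted.** It also protects against data-driven re-sizing: under A at 114 per arm, testing stage 2 at 0.05 would give about 7.5% false positives instead of 4.7%.

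**Cited method.** The rule is footnoted to a published two-stage method. The documents do not reproduce it, so whether it supplies the missing step cannot be judged from them.

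**Conclusion.** The point holds as an internal conflict with an undefined gate. The stated purpose and the written branches can give opposite decisions on the same data, and an unspecified power calculation decides which applies. If the branches are followed literally and the design assumptions hold, 30% (A) or 36% (B) of trials at 114 per arm meet the 95% bound and are still extended; at 152 per arm the figures are 24% or about 0%. The consequence is avoidable enrolment and delay, plus, at 114 per arm with the gate at α = 0.05, a 1–2% chance of losing a result already met. The documents do not support a claim that overall power is lost. The sizes rest on effect 0.292, SD 0.802, approximate normality and the two readings of calculated power.

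**What to change.** In Protocol 9.1, Protocol 9.9 and SAP 12:

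1. State that if calculated power is below 80%, the one-sided 97.06% interval is first built from stage-1 data in the primary-analysis population. If its lower bound exceeds δ, superiority is confirmed and the trial ends. Only otherwise is the size recalculated at α = 0.0294, with a pooled 97.06% interval.
2. Define calculated power: effect, SD, α and population.
3. Use the same effect for gate and re-sizing. Either use the planned 0.265 with observed SD (simulated false-positive rate about 4.7–5.0%), or the observed effect with total size capped at twice stage 1 (about 4.9%; about 6.2% uncapped). Do not pair an observed-effect gate with planned-effect re-sizing: overall success would be about 82–84%, and the recalculated size often would not exceed the number already enrolled (with SD 0.802 it is 2 × 2.731² × 0.802²/0.265² ≈ 137 per arm, below 152).
4. State what happens when the recalculated size does not exceed the number enrolled.
5. Beside the 80% in Protocol 9.1, note that it is the power of the single-stage test.
6. Remove the SAP 9 statement that there are no interim analyses.

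Cost: wording only, with no added patients. At 114 per arm stage-1 success rises to about 73% (A) or 76% (B). The downside is a slightly higher false-positive rate, still within about 5%.
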